#### 4.13 Determination of Sample Size

No formal testing of hypotheses has been planned for this study. Therefore, no formal sample size calculations were performed. 45 subjects are considered to be adequate to analyze the study objectives.

#### 4.14 Interim Analyses

There will be two interim analyses (IAs) before general database lock and provision of final study results.

Each interim analyses will be preceded by a DRM focusing on the subjects to be included in the actual IA, i.e. for the first interim analysis (Deliverable 1) the target subject pool will be those who were enrolled for Arm 1 – 3 (Adults), for the second interim analysis (Deliverable 2) the target pool will be those who were enrolled for Arm 4 – 6 (Elderlies).

The first interim analysis will use data collected in Arm 1 – 3 up to the last subject in Arm-3 completed its Week 4 visit (Adults, highest dose). The second interim analysis will use data collected in Arm 4 – 6 up to last subject in Arm-6 completed its Week 4 visit (Elderlies, highest dose).

All outputs specified in the study's TLF Specification will be provided for both IAs. Grouping of IA summaries will follow guidelines specified in Section 4.2.1.

Selected immunogenicity endpoints such as ELISpot and nAb data will be analyzed at single timepoints during interim analyses. Results of ELISpot and nAb will be reported only for Week 2 and Week 4, respectively.

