4.2.5. Deliverables

- 1. Within five months after the study approval a report on safety and immunogenicity at 4 weeks for Adult-Cohort will be developed; this report will include:
 - a. an analysis of safety issue in the three adults-arms
 - b. pivotal consideration used for authorizing enrollment in the Elderlies-Cohort
 - c. a preliminary analysis of immunogenicity in the three adults-arms aimed at identifying the most convenient doses to be used in the eventual phase 2/3 trial.
- 2. Within seven months after the study approval a report on safety and immunogenicity at 4 weeks for Elderly-Cohort will be developed; this report will include pivotal consideration on
 - a. an analysis of safety issue in the three elderlies-arms
 - b. a preliminary analysis of immunogenicity in the three elderlies-arms aimed at identifying the most convenient doses to be used in the eventual phase 2/3 trial.
 - c. comparison of safety and immunogenicity between adults and elderlies (across the cohort comparison) to define the most convenient doses to be used either in general population or special groups at risk.
- 3. Within one year since study approval final report will be produced including:
 - a. Final analysis on safety and immunogenicity at 24 weeks after vaccination in Adults-Cohort
 - b. Final analysis on safety and immunogenicity at 24 weeks after vaccination in Elderlies-Cohort

[figure not shown]

Figure 6 Estimated time (week) for enrollment and follow-up for Adults-Cohort. Figures within cells represent time (in weeks) after vaccination. Grey bars represent timing of authorization for enrollment. Blue cells represent time of participants' enrollment. Emerald green cells represent time for safety assessment. Golden cells represent time of sampling carried out for immunogenicity assay on frozen specimens. Red cells represent time of sampling carried out for immunogenicity assay on fresh samples. Orange cells represent milestones (letters represent the specific milestone). Olive green cells represent deliverables (numbers represent the specific deliverable).

[figure not shown]

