## 1 INTRODUCTION

The analyses described in this SAP are based upon the following study documents:

- Study Protocol, Version 2.0 (September 8, 2020)
- electronic Case Report Form (eCRF), Version 4 (generated on August 4, 2020)
- DSMB Charter, Version 2.0

Per protocol, the collected data will be analyzed and reported in three steps according to stages achieved during the course of the study, ie:

Delivery 1: Interim Analysis 1

A report on safety and immunogenicity at 4 weeks for Adults-Cohort will be developed; this report will include:

- a. an analysis of safety issue in the three adults-arms;
- b. pivotal considerations for authorizing enrollment in the Elderlies-Cohort;
- c. a preliminary analysis of immunogenicity in the three adults-arms aimed at identifying the most convenient dose to be used in the eventual phase 2/3 trial.

Delivery 2: Interim Analysis 2

A report on safety and immunogenicity at 4 weeks for Elderlies-Cohort will be developed; this report will include pivotal considerations on:

- a. an analysis of safety issues in the three elderlies-arms
- b. a preliminary analysis of immunogenicity in the three elderlies-arms aimed at identifying the most convenient doses to be used in the eventual phase 2/3 trial.
- c. comparison of safety and immunogenicity between adults and elderlies (across the cohort comparison) to define the most convenient dose to be used either in general population or special groups at risk.

Delivery 3: Final Analysis

Within one year since LSLV final report will be produced including:

- a. Final analysis on safety and immunogenicity at 24 weeks after vaccination in Adults-Cohort
- b. Final analysis on safety and immunogenicity at 24 weeks after vaccination in Elderlies-Cohort

Analyses described hereafter will cover all these three stages of the study with applicable closures on selected analyses if a stage requires.

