**Table 2 Grouping: Subject Classification, Disposition, Demographics, Exposure, AEs and Categorical Safety**

Delivery									
IA 1	Arm-1	Arm-2	Arm-3	Total					
IA 2	Arm-4	Arm-5	Arm-6	Total					
FA	Arm-1	Arm-2	Arm-3	Arm-4	Arm-5	Arm-6	Total		
FA [1]	Arm-1	Arm-2	Arm-3	Adult Total	Arm-4	Arm-5	Arm-6	Elderly Total	Total

IA: Interim analysis. FA: Final analysis.

[1] AE and Categorical Safety only

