**Table 3 Grouping: Safety (excluding AEs and Categorical Safety), Immunogenicity, Labs and Diary Data**

Delivery						
IA 1	Arm-1	Arm-2	Arm-3			
IA 2	Arm-4	Arm-5	Arm-6			
FA	Arm-1	Arm-2	Arm-3	Arm-4	Arm-5	Arm-6

IA: Interim analysis. FA: Final analysis.

For interest of space table displays treatment arms instead of treatment labels, but outputs will display treatment labels.

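### Interim Analysis 2 is required to compare adults with elderlies, but its data scope and table columns include no adult arm; a smaller, related point is unequal follow-up by dose in interim summaries that have no fixed window

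*SAP*

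**What the plan says.** **What IA2 must deliver.** SAP section 1 lists, as item c of Delivery 2, a "comparison of safety and immunogenicity between adults and elderlies (across the cohort comparison) to define the most convenient dose" for the general population or for groups at special risk. Protocol 4.2.5 sets the same task for its second deliverable: "comparison of safety and immunogenicity between adults and elderlies (across the cohort comparison) to define the most convenient doses". Protocol 10.2, item D, names the pairs: Arm 1 with 4, Arm 2 with 5, Arm 3 with 6.

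**What IA2 contains.** SAP 4.14 says "The second interim analysis will use data collected in Arm 4" to 6, and its data review meeting covers the same subjects. The section also ties the grouping of interim summaries to SAP 4.2.1. There, Table 2 ("Grouping: Subject Classification, Disposition, Demographics, Exposure, AEs and Categorical Safety") gives IA2 the columns Arm-4, Arm-5, Arm-6 and Total. Table 3 ("Grouping: Safety (excluding AEs and Categorical Safety), Immunogenicity, Labs and Diary Data") gives it Arm-4, Arm-5 and Arm-6.

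**When the data are cut.** IA1 uses Arms 1-3 "up to the last subject in Arm-3 completed its Week 4 visit". IA2 has the parallel rule for Arms 4-6, ending with the last Arm-6 subject's Week 4 visit. No cut at the individual subject's own Week 4 visit is stated.

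**The concern.** The output that is meant to inform the phase 2/3 dose for older and younger people has no table in the plan. Someone preparing it would have to set the adult interim report beside the elderly one, and nothing in the SAP says how, or that adult results are carried forward. The two reports come from separate data review meetings. The SAP revision history also records that the handling of results below the detection or quantification limit was added in version 2.0 and updated in version 4.0. The interim dates are not given, so the two reports may or may not have been run under the same rules.

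The cut raises a second, lesser matter. Arms enrol in order of dose, and each cut waits for the highest dose to reach Week 4. Lower doses therefore bring more follow-up. Where a summary takes the worst or maximum value over all available data, extra visits add chances of an abnormal result at the lower doses, which works against seeing a dose-related effect.

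**Working it through.** **1. Required content against specified content**

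| Item | Adult arms | Elderly arms |
|---|---|---|
| Delivery 2, item c (SAP 1; protocol 4.2.5) | needed | needed |
| IA2 pool and data (SAP 4.14) | none | Arms 4-6 |
| Table 2, IA2 row | none | Arms 4-6, Total |
| Table 3, IA2 row | none | Arms 4-6 |
| Tables 2 and 3, final analysis rows | Arms 1-3 | Arms 4-6 |

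IA2 has 0 of 3 adult arms. The two cohorts share a table only at the final analysis.

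**2. Follow-up at the interim cut**

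The documents give no per-arm follow-up, and the planned calendar (protocol Figures 6 and 7) is not shown, so the calendar below is an assumption.

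Inputs from protocol sections 5 and 7.7: group A has 3 subjects and group B has 12, each enrolled over a week; the next step waits for 7-day safety. Assumed base case: a 14-day step (enrolment week plus safety week), group A vaccinated on days 0, 2 and 4 of its week (mean 2), group B spread evenly over days 0-6 (mean 3). Cut = last highest-dose vaccination + 28 days.

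- Cut: 3 × 14 + 6 + 28 = day 76.
- Mean vaccination day, lowest dose: (3 × 2 + 12 × 17)/15 = 14. Follow-up 76 − 14 = 62 days.
- Intermediate: (3 × 16 + 12 × 31)/15 = 28. Follow-up 48 days.
- Highest: (3 × 30 + 12 × 45)/15 = 42. Follow-up 34 days.
- Ratios to the highest dose: 62/34 = 1.82 and 48/34 = 1.41.

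The range uses a 10-day step (group A on days 0, 2, 2; group B over days 0-4) and a 21-day step (one further week for review).

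| Step | Cut (day) | Mean weeks: low, intermediate, high | Low/high | Intermediate/high | Reached 56 days: low, intermediate, high (of 15) |
|---|---|---|---|---|---|
| 10 days | 62 | 7.4, 6.0, 4.6 | 1.62 | 1.31 | 3, 0, 0 |
| 14 days | 76 | 8.9, 6.9, 4.9 | 1.82 | 1.41 | 15, 3, 0 |
| 21 days | 97 | 11.1, 8.1, 5.1 | 2.19 | 1.59 | 15, 3, 0 |

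These figures apply to IA1, and to IA2 if the elderly sequence runs in parallel. However, protocol section 5 and SAP 3.1 make Arm-6 group B depend on Arm-5 group A, whereas Arm-3 group B depends on Arm-3 group A. Protocol 4.2.4 and SAP 4.11.7 list separate decisions for Arm-6 groups A and B, and protocol 7.7 says that the elderly cohort follows the adult scheme. If the Arm-6 condition is taken as written, the base-case IA2 cut is day 62, with mean follow-up of 6.9, 4.9 and 4.5 weeks and ratios of 1.54 and 1.09 (1.40-1.81 and 1.07-1.13 over the same steps).

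**3. Which outputs this touches**

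Equal windows already apply to treatment-emergent AEs (28 days), solicited reactions (7 days), the diary (4 weeks), ELISpot (Week 2), neutralising antibody (Week 4) and all by-visit tables. No fixed window applies to AESI counts, overall CTCAE grade, worst post-baseline laboratory value, maximum liver value and the eDISH plot, or overall vital-sign grades.

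Scheduled post-baseline blood draws are D2, W1, W2 and W4 (four), then W8 (five). With per-draw abnormal rate *p*, independent draws and no dose effect, P(any abnormal) = 1 − (1 − *p*)^k:

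| Assumed *p* | k = 5 | k = 4 | Difference in subjects per arm of 15 |
|---|---|---|---|
| 1% | 4.9% | 3.9% | 0.14 |
| 5% | 22.6% | 18.5% | 0.6 |
| 10% | 41.0% | 34.4% | 0.98 |

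**4. Are adult Week 4 data available at IA2?**

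In the base case the last Arm-1 vaccination is day 14 + 6 = 20, so its Week 4 visit is day 48. If Arm 4 starts then, the IA2 cut is day 48 + 76 = 124, or 48 + 62 = 110 with the Arm-6 condition as written. Adult Week 4 data are complete at day 76, so they precede IA2 by 34 to 48 days.

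**The case against.** SAP 4.14 promises the full set of specified outputs at both interims, so IA1 already supplies the same tables for adults. The cut rule is the same in both, and most windows match. The trial is descriptive with no hypothesis tests, and the final analysis shows all six arms together. On this view nothing is estimated wrongly; only a side-by-side layout is missing.

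Much of that stands. A reader might infer that the comparison is impossible, or that the two reports rest on incompatible cuts; the documents support neither. But reading across reports is nowhere specified, and a descriptive comparison still needs both groups. The final analysis does not replace it either: the plan places this dose comparison at the second delivery, and protocol 4.1 aims for phase 2/3 at the beginning of 2021.

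On follow-up, a reader might infer that both interim cuts give the lower doses about twice the highest dose's follow-up, and that all earlier arms bring Week 8 data. The calendar does not bear this out. About twice fits only the lowest dose. In the base case 12 of 15 intermediate-dose subjects have not reached day 56, and the IA2 ratios depend on an unresolved enrolment condition. Nor do the documents show that toxicity would be hidden: the contrast is five draws against four, within-person correlation would usually narrow it, and by-visit CTCAE tables offer a like-for-like view at Week 4.

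**Conclusion.** The main point holds on the text alone and needs no assumption: IA2 is required to compare adults with elderlies, and neither its data scope nor either table layout includes an adult arm. This is a gap in specification, not a biased estimate.

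The follow-up point holds in direction but is small. At IA1 the lowest dose has roughly 1.6-2.2 times and the intermediate dose roughly 1.3-1.6 times the highest dose's follow-up; at IA2 the imbalance is similar, or about 1.5 and 1.1 with the Arm-6 condition as written. It affects only the summaries without a fixed window, by less than one subject per arm of 15 at per-draw rates of 1% to 10%. These sizes rest on the assumed calendar, independent draws and the assumed rates. The five-against-four contrast applies to the whole lowest-dose arm in the 14-day base case. On the 10-day step only 3 of its 15 subjects have reached day 56. On the 21-day step all 15 have, and 3 have also reached day 77 (Week 12).

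**What to change.** - In SAP 4.14 and the IA2 rows of Tables 2 and 3, add Arms 1-3, using adult data through each subject's own Week 4 visit. Place same-dose columns side by side: Arm 1 with 4, 2 with 5, 3 with 6.
- At both interims, base the AESI, overall CTCAE, worst laboratory, maximum liver, eDISH and overall vital-sign summaries on data through each subject's own Week 4 visit. List later data separately so that no safety information is lost. The 28-day AE tables need no change.
- Reconcile the passages on authorising Arm-6 group B (protocol 4.2.4, 5 and 7.7; SAP 3.1 and 4.11.7).

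The cost is SAP wording and table shells, or one supplementary table set if IA2 has already run. No new data collection is needed.

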#### **4.15 Changes in the Conduct of the Study or Planned Analysis**

In reflection to DSMB recommendations on the meeting held 3rd October 2020, additional analyses on liver enzyme data will be performed with categorized liver test results and standard eDISH plot.

## 6 APPENDICES

### 6.1 Schedule of Assessments

**Table 5 Schedule of Assessments**

	Time of the visit since vaccination									
	Screening	T0	D2	W1	W2	W4	W8	W12	W24	
Window (days)	≤ 28	0	0	±1	±1	±2	±4	±7	±14	
Informed consent	X									
Eligibility	X									
Vaccination		X								
AE reporting	X	X	X	X	X	X	X	X	X	
Diary card		A		B	B	B§				
Checking diary card completeness			X	X	X	X				
Medical history										
Adverse Events	X	X	X	X	X	X	X	X	X	
Concomitant Medications	X	X	X	X	X	X	X	X	X	
Physical examination	X	X	X	X	X	X	X	X	X	
Body Temperature	X	X	X	X	X	X	X	X	X	
SpO2 %	X	X	X	X	X	X	X	X	X	
Pulse	X	X	X	X	X	X	X	X	X	
Blood pressure	X	X	X	X	X	X	X	X	X	
ECG	X									
Urine analysis	X									
Urine B-HCG	X	X								
Blood counts	X	X	X	X	X	X	X	X	X	
Biochemistry	X	X	X	X	X	X	X	X	X	
Coagulation	X									
HIV-Ab	X									
HBsAg and HCV	X									
HLA Typing				X						
SARS-CoV-2 Serology*	X									
CLIA anti-S (IgG)		X		X	X	X	X	X	X	
CLIA anti-N (IgG)		X		X	X	X	X	X	X	

# Parexel International

ReiThera SRL.

RT-CoV-2

Statistical Analysis Plan

	Time of the visit since vaccination									
	Screening	T0	D2	W1	W2	W4	W8	W12	W24	
Micro neutralization						X			X	
ELISpot SARS-CoV-2		X			X	X	X	X	X	

Scr=screening to be done no more than 21 days before vaccination; T0= day of the vaccination; D2= day 2 after vaccination; W1= one week after vaccination; W2= two weeks after vaccination W4= four weeks after vaccination; W8= eight weeks after vaccination; W12= twelve weeks after vaccination; W24= twenty-four weeks after vaccination. A) Diary given to volunteers; B) Diary received from volunteers. §At week 4, diary cards for W3 and W4 will be collected.

\* This is any serological assay to detect anti-SARS-CoV-2 total IgG which is validated for clinical use in Italy (i.e. validated for diagnosis of SARS-CoV-2 infection). †no CRP testing at screening.

TP-GDO-WW-133-02

CONFIDENTIAL

Project Document Version No. 4.0

Effective Date: 26 Nov 19

Project Document Effective Date: 23-Jun-2021

Related to: SOP-GDO-WW-019

Page 33 of 33

Signature Page for VV-TMF-289681 v4.0

Reason for signing: Approved	Name: [name] Role: Biostatistics Date of signature: 23-Jun-2021 15:32:54 GMT+0000
------------------------------	---

Reason for signing: Approved	Name: [name] Role: Sponsor Date of signature: 24-Jun-2021 09:25:42 GMT+0000
------------------------------	---

Reason for signing: Approved	Name: [name] Role: Sponsor Date of signature: 28-Jun-2021 08:32:34 GMT+0000
------------------------------	--

Signature Page for VV-TMF-289681 v4.0
